Identical test days will take place before the initial weight loss phase (V0, week -8), after initial weight loss (V1, week 0) and after 52 weeks of treatment (V3). For details on test days, see study protocol (1).

Weight consultations will be performed weekly during initial VLCD phase and at week 1, 2, 3, 4, 9, 13, 17, 22, 26, 32, 39 and 46. Fasting blood samples will be collected at week 4, 13, 26 and 39.

Finally, participants will be invited to complete a post-trial unsupervised follow-up visit (V4) 1 year after intervention completion.

10 Randomization

After the initial eight-week VLCD phase, participants will be randomized after the test day (V1) to one of the four study groups in a 1:1:1:1 ratio in accordance with a subject randomization list (SRL) provided by Novo Nordisk. An un-blinded study nurse (not otherwise associated with the trial) will allocate study participants according to the SRL. Randomization will be stratified by sex (male/female) and age (below/above 40 years).

11 Sample size

Sample size calculation for total body weight:

Sample size for primary endpoint was calculated in relation to total body weight. Based on previous weight loss studies with liraglutide (15,49), we estimate the response within each treatment group to be normally distributed with a standard deviation of 5.5 kg. Thus, with 30 participants completing each study arm we will be able to detect a difference in delta of 4 kg between groups with a power of 0.8, assuming a two-sided α -level of 0.05. We will need 34 completers in each arm in order to attain a statistical power of 0.85 and 40 completers in each arm to attain a statistical power of 0.90. In our previous study, 10 % of participants who entered the initial VLCD phase did not complete this phase (15). With 222 recruited study participants and an expected dropout rate of 25 % after randomization, we expect to have at least 30 participants from each study arm to complete the trial.

Sample size for total body fat percentage

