- Food preference questionnaire (LFPQ) and subjective appetite sensation
- Faecal bacterial composition
- Plasma metabolomics and proteomics
- Epigenetics of spermatozoa
- Questionnaires (TFEQ, IPAQ, G-SES, PSQI)

Outcomes measured at other time points:

- Body weight (week -7, -6, -5, -4, -3, -2, -1, 1, 2, 4, 9, 13, 17, 22, 26, 32, 39, 46 and V4)
- Number/proportion of participants that have reduced total body weight by $\geq 5\%$, $\geq 10\%$ and $\geq 15\%$ at V3 compared with V0
- Body composition (V0 and V4)
- Metabolic health (week 4, 13, 26, 39 and V4)
- Safety (adverse events) (week 1, 2, 3, 4, 9, 13, 17, 22, 26, 32, 39 and 46)
- Meal related appetite response (V0)
- Peak oxygen uptake, stair test and maximal isometric strength test (V0)
- Systemic markers of immune-metabolism and oxidation (V0)
- Endothelial function (V0)
- Immuno-metabolic changes in the subcutaneous adipose tissue (V0 and week 26)
- Gene expression profile of circulating inflammatory cells (V0)
- Bone health (V0 and V4)
- Food preference questionnaire (LFPQ) (V0 and V4) and subjective appetite sensation (V0)
- Faecal bacterial composition (V0)
- Plasma metabolomics and proteomics (V0, week 4, 13, 26, 39 and V4)
- Epigenetics of spermatozoa (V0)
- Questionnaires (SF-36, TFEQ, IPAQ, G-SES, PSQI) (V0 and V4)
- Measurement of sleep and physical activity levels (V0, week 13, 26 and V4)

27 Analysis methods

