Analyses of primary and secondary outcome (except for the pre-planned sensitivity analyses) will be performed based on the intention-to-treat (ITT) principle. All continuous endpoints/outcomes will be modelled using linear mixed effects models with the following fixed effects and interactions: Time (factorial), Treatment, Time (factorial)*Treatment, sex (female, male) and age group (<40 years, >40 years). The models will be specified with a restricted maximum likelihood estimation method, the Kenward-Roger degrees of freedom method, an unstructured covariance structure and a [repeated effect for visit random intercept on participant level](#). Model fit will be evaluated using graphical methods and if necessary, outcomes will be log-transformed. Estimated mean differences (CI95%) for changes between groups (main study effects), conditional means (CI95%), and within group changes (CI95%) will be extracted from the model. For log-transformed outcomes the results will be back-transformed and be presented as the ratio between estimated relative changes (CI95%), estimated conditional geometric means (CI95%) and within group relative changes (CI95%), respectively. Between group differences in changes will be null-hypothesis tested and presented with P-values.

The following predefined sensitivity analyses will be performed for the primary and secondary outcome; an additional ITT analysis with adjustment for initial weight loss, an ITT analysis using multiple imputation to assess effects of missing data (see also 28), and finally an analysis of per protocol completers.

The analysis of the primary and secondary outcome will be performed blinded to group allocation by a researcher ([name]) that have not been involved in the execution of the trial. The statistical and clinical/physiological implications of the results will be evaluated by the research team before un-blinding.

28 Missing data

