The number/frequency of missing values for the primary and secondary outcome in each group at each time point will be provided. For the main analysis, the results will be based on likelihood inference and missing data will be assumed to be missing completely at random or missing at random. An additional analysis based on multiple imputation of missing values will be performed (see also 27). The dataset used for the imputations will include all observations for total body weight measured at or between V1-V3, and the auxiliary variables Sex (male or female) and Age (continuous, years). Under the assumption that weight changes in participants after loss to follow-up would resemble the development in the placebo groups rather than the development in the group to which they were originally randomized, the participants with missing values at V3 will be pooled with the placebo group and using a Markov chain Monte Carlo method all missing values will be imputed, assuming a multivariate normal distribution for the data, to create 1000 new datasets. Subsequently, the imputed datasets will be analyzed using the same mixed linear model used for the main analysis and averaged estimates calculated. If the main outcome has been transformed to fit the statistical model used for the main analysis this transformation will be applied in the imputation procedure.

29 Additional analyses

Not relevant

30 Harms

Adverse events (defined in the trial protocol) with an incident of $\geq 5\%$ in any treatment group and all serious adverse events will be reported by system organ class and preferred term for participants in all four treatment groups separately and for liraglutide pooled (exercise and non-exercise) and placebo pooled (exercise and non-exercise). Events will be reported as the number of and percentage of individuals experiencing an adverse event. Rates of adverse events will not be compared by null-hypothesis testing.

31 Statistical software

R version 3.6.0 or newer version (The R Foundation for Statistical Computing, www.R-project.org) and SAS version 9.4 or newer version (SAS Institute, Cary, NC, USA).

References

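### The primary model does not use sex, age group or V1 weight to sharpen the V1-to-V3 contrast, and the initial-weight-loss adjustment has no stated form

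*SAP*

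**What the plan says.** Item 27 lists the fixed effects of the linear mixed model as "Time (factorial), Treatment, Time (factorial)*Treatment, sex (female, male) and age group (<40 years, >40 years", with REML, an unstructured covariance and Kenward-Roger degrees of freedom. Sex and age group have no interaction with time, and the V1 value is not a covariate.

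V1 is a response in this model. Between-group differences in change are the main study effects, and "within group changes (CI95%) will be extracted from the model". Item 28 says that the imputation data contain "all observations for total body weight measured at or between V1-V3" and that "the imputed datasets will be analyzed using the same mixed linear model used for the main analysis". Treatment together with its interaction with time therefore gives each arm its own V1 mean, although item 10 places randomization after the V1 test day.

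Item 10 also states: "Randomization will be stratified by sex (male/female) and age (below/above 40 years". Item 11 bases the sample size on the change in weight, taken as "normally distributed with a standard deviation of 5.5 kg", without covariate adjustment.

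Among the sensitivity analyses item 27 names "an additional ITT analysis with adjustment for initial weight loss", for the primary and the secondary outcome. It does not give the scale (kg or percent) or say whether the covariate interacts with time.

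**The concern.** Sex and age group look like an adjustment for the stratification factors, but for a V1-to-V3 contrast a time-constant term does no such work. The randomization makes expected V1 means equal across arms, and the model does not use that fact either. The primary contrast then carries variance that could have been removed. Because allocation is stratified, the reported standard error is also somewhat larger than the true sampling variability whenever regain differs by sex or age.

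Interval width matters most for the non-inferiority hypotheses (3, 4 and 8 in item 8), which are decided by an upper confidence limit. Under items 16-18 a failed hypothesis also makes all later tests exploratory.

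The initial-weight-loss analysis has a different problem. If that covariate is added in the same way as sex and age group, the analysis would agree with the main result by construction and could be reported as evidence of robustness.

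**Working it through.** **1. The plan's own figures.** Inputs from item 11: SD 5.5 kg, difference 4 kg, two-sided alpha 0.05. With n = 2(z₀.₉₇₅ + z_power)² × 5.5² / 4² per arm:

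- power 0.80: 2 × 7.849 × 30.25 / 16 = 29.7, so 30
- power 0.85: 2 × 8.978 × 30.25 / 16 = 33.9, so 34
- power 0.90: 2 × 10.507 × 30.25 / 16 = 39.7, so 40

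These match the plan. They use the unadjusted SD of change, so they do not depend on the adjustment.

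**2. Algebra.** Write weight of participant i in arm a at visit t as μ_t + τ_at + β·sex + γ·age group + e_it. Then

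change = (μ_V3 − μ_V1) + (τ_a,V3 − τ_a,V1) + (e_V3 − e_V1).

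β and γ cancel. Under an unstructured covariance the data split into the changes from V1 and V1 given those changes. The first part contains only free arm-by-visit means. In the second part the arm means are also free, so it carries no information about the contrast. With complete data the estimate must be the raw difference in mean change, whatever sex and age do. If instead all arms share one V1 mean, the estimate becomes approximately (difference in mean change) − b × (difference in V1 mean), where b is the slope of change on V1, and its variance falls by a factor of about 1 − r².

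**3. Numerical check.** REML fits to complete simulated data (2 visits, 400 trials; 13 visits, 40 trials) gave these maximum differences:

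- model with sex and age group versus without: 0.000000, in both estimate and SE
- model versus raw difference in change: 0.000000
- initial weight loss as a main effect versus the main model: 0.000000

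A separate generalised-least-squares check gave the same identity.

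**4. Precision lost.** From the SAP: SD of change 5.5 kg, 25% dropout, 222 × 0.9 / 4 ≈ 50 randomized per arm, and weight at V1, the 11 intermediate visits in item 26 ("1, 2, 4, 9, 13, 17, 22, 26, 32, 39, 46 and V4", leaving out V4) and V3, which makes 13 visits. Assumed: V1 SD 14 kg, arms balanced on sex and age, monotone dropout missing at random, the correlation r of V1 weight with change, and the sex difference in regain. Each scenario had 150 trials, without the Kenward-Roger correction. Percentages are from unrounded values.

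| Assumption | Mean SE as written | With time interactions and common V1 mean | Change |
|---|---|---|---|
| No covariate predicts change | 1.205 | 1.204 | −0.15% |
| r = −0.1, 1 kg sex difference | 1.203 | 1.191 | about −1% |
| r = −0.25, 2 kg sex difference | 1.196 | 1.138 | −4.9% |

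In the last row the time interactions alone give 1.173 (−1.9%) and the common V1 mean alone 1.159 (−3.1%). The latter agrees with 1 − √(1 − 0.25²) = 3.2%. The 95% half-width goes from 1.96 × 1.196 = 2.34 kg to 1.96 × 1.138 = 2.23 kg. For body fat percentage (2 visits, SD 2.1; r = −0.25 and a 0.8-point sex difference assumed) the SE goes from 0.480 to 0.457 (−4.8%).

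In power terms the residual SD is 5.5√(1 − R²). An assumed R² of 0.05 gives 5.36 kg, and 0.10 gives 5.22 kg. Power at 30 completers per arm moves from 0.804 to 0.824 and 0.844.

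**5. Reported versus true variability.** With 2 visits, complete data and the stronger scenario, the mean reported SE as written is 1.095 against a sampling SD of 1.066. With time interactions it is 1.072 against 1.066. Under stratified allocation the interactions correct the reported SE and leave the sampling SD unchanged.

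**6. Initial weight loss.** With an assumed slope of 0.4 kg regained per kg lost and 25% dropout, entry as a main effect moved the contrast by at most 0.08 kg. Entry by time moved it by up to 0.98 kg (95th percentile 0.53 kg). The SAP's minimal important difference is 4 kg.

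**The case against.** The strongest reply is that this is a preference. A repeated-measures model with free baseline means is valid, the trial was powered on unadjusted change, and the SAP nowhere claims that sex and age group add precision. It also has slack: 222 × 0.9 × 0.75 / 4 ≈ 37 completers per arm against 30 needed, or power of about 0.88 for 4 kg. That all stands, which is why the point is one of efficiency.

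The gain rests on correlations that the SAP does not give, and it could be nil. With a true difference of zero and the +4 kg margin, power for hypotheses 3 and 4 is Φ(4/SE − 1.96). It moves from 0.917 to 0.940 in the stronger scenario and stays at 0.913 when nothing predicts change. The time interactions also leave the sampling SD where it was; the real gain in precision comes from the common V1 mean. This stands too, but a reported SE about 2.7% too large (1.095 / 1.066) still widens the interval on which non-inferiority is judged.

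The simulation omitted Kenward-Roger, and the number of weight visits is not settled: item 26 implies 13, item 15 omits week 32, and item 9 adds week 3. The parameter counts would shift slightly; the algebra would not.

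Finally, the initial-weight-loss analysis is only one of three sensitivity analyses, and the SAP does not actually state the main-effect reading. That is fair, but the only covariates whose form is stated enter as main effects, so it is a natural reading.

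**Conclusion.** The concern holds. As written, sex and age group do nothing for the complete-data V1-to-V3 contrast and very little with 25% dropout. In the stronger scenario they moved the estimate by at most 0.23 kg (95th percentile 0.14 kg) against the same model without them. V1 weight is not used against chance imbalance.

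The cost is lost precision: nil to about 5% of the standard error over the assumed range (r from 0 to −0.25, sex difference from 0 to 2 kg). There is no bias, no inflation of type I error and no error in the sample size.

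The undefined initial-weight-loss term is the more consequential part, because its form decides whether that sensitivity analysis can disagree with the main result at all.

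**What to change.** In item 27:

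- Add Time × sex and Time × age group, with age group coded as on the randomization list. The listed categories do not place a participant aged exactly 40.
- Constrain the arms to a common V1 mean by entering treatment terms only at visits after V1. Alternatively, keep only post-V1 visits as responses and add V1 value × Time as a covariate.
- State that initial weight loss enters its sensitivity analysis as Time × initial weight loss, and on which scale.

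The cost is SAP wording and no new data. With 13 weight visits the fixed effects go from 4 × 13 + 2 = 54 to 54 + 24 − 3 = 75, next to 13 × 14 / 2 = 91 covariance parameters, and the initial-weight-loss analysis adds 12. For body fat percentage at V1 and V3 it is one extra term per covariate. If no covariate predicts change, the 24 interactions raised the mean SE by 0.07% in simulation, before any Kenward-Roger correction.
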